5.2.2. Definition of Dose Limiting Toxicities

The following DLT criteria apply only to Phase 1b of the study. After completing the DLT period (28 days), Phase 1b subjects will be evaluated by standard safety reporting.

A DLT is defined as any drug-related hematologic or non-hematologic toxicity Grade 3 or higher, with the following exceptions:

- Grade 4 nausea, vomiting, or diarrhea or Grade 3 diarrhea defined by ≥ 7 stools/day persisting for greater than 3 days despite best supportive care
- Grade 4 neutropenia or Grade 3 neutropenia persisting for greater than 14 days or Grade 3 neutropenia of any duration with fever
- For subjects with Grade 2 rash at entry, DLT will be progression to Grade 3 AND a doubling of % BSA involvement
- For subjects with Grade 3 rash at entry, DLT will be progression to Grade 4 OR a doubling of % BSA involvement

5.2.3. Phase 2

Following the establishment of the RP2D, the Phase 2 portion of the study will begin accruing additional subjects. Approximately 40 subjects (cumulative from both Phase 1b and Phase 2) will be treated with the RP2D. Subjects enrolled in the Phase 2 part of the study will have met the same inclusion/exclusion criteria as Phase 1b subjects and will be treated with the RP2D. Subjects continuing from Phase 1b and subjects enrolled in Phase 2 will continue to be treated unless they have intervening unacceptable toxicity or meet other criteria for subject discontinuation (see [Section 9](#)).

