	
 • If 3 DLTs are observed, then the dose level will be stopped and the next lower dose will be assessed. 
If a subject experiences a DLT during the DLT observation window, the subject will discontinue treatment and not be replaced in that dose level.
 
The decision to proceed with a RP2D or to dose reduce will be made in a Dose Level Review Meeting by the Sponsor in conjunction with representative investigators after consideration of all available safety and laboratory information.
 
A dose limiting toxicity (DLT) is defined as any drug-related hematologic or non-hematologic toxicity Grade 3 or higher, with the following exceptions:
 
 • Grade 4 nausea, vomiting, or diarrhea or Grade 3 diarrhea defined by ≥ 7 stools/day persisting for 3 days despite best supportive care • Grade 4 neutropenia or Grade 3 neutropenia persisting for 14 days or Grade 3 neutropenia of any duration with fever • For subjects with Grade 2 rash at entry, DLT will be progression to Grade 3 AND a doubling of % BSA involvement • For subjects with Grade 3 rash at entry, DLT will be progression to Grade 4 OR a doubling of % BSA involvement 
Phase 2:
 
Following the establishment of the RP2D, the Phase 2 portion of the study will begin accruing additional subjects. Approximately 40 subjects (cumulative from both Phase 1b and Phase 2) will be treated with the RP2D.

Concomitant Therapy:	Refer to Section 6 for information on concomitant therapy.
Safety Plan:	This study will be monitored in accordance with the Sponsor's Pharmacovigilance Committee procedures. Adverse events (AEs) and serious adverse events (SAEs) will be reviewed by the Sponsor on an ongoing basis to identify safety concerns per the Medical Monitoring Plan.

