5.2. Study Treatment

5.2.1. Phase 1b Dose Selection and Stopping Rules

Three dose levels of ibrutinib may be tested: 140 mg/day, 280 mg/day and 420 mg/day. The starting dose will be 420 mg/day and the dose will be modified based on the dose limiting toxicities (DLTs).

Phase 1b will follow a modified 3+3+3 design with 6-9 subjects at each dose level. The dose will be selected as the RP2D if the subject incidence of DLTs during the first 28 days of study treatment is <33%. Before determining the RP2D, 6 subjects in any given cohort must have completed the DLT observation period which is defined as 28 days of therapy. Using the modified 3+3+3 design, the maximum tolerated dose (MTD) is exceeded when ≥ 3 out of 9 subjects in a dose level experience a DLT. If there are 3 DLTs at a dose level, the MTD is exceeded and then the next lower dose level will be enrolled.

Enrollment in a dose level will proceed as follows:

- If no DLT is observed during the DLT observation period in the initial 3 subjects of a dose level, then a second group of 3 subjects will be enrolled at the same dose level for a total of 6 subjects. If 0-1 DLT occur out of 6 subjects, then this dose will be the RP2D. If 2 DLTs occur out of 6, then the dose level cohort will be expanded to enroll a total of 9 subjects. If no further DLTs occur then this dose will be the RP2D.
- If 1 DLT is observed in the initial 3 subjects, the dose level will be expanded to enroll 3 additional subjects at the same dose level for a total of at least 6 subjects. If no further DLT(s) are observed, then this dose will be the RP2D. If 2 DLTs are observed out of 6 subjects, then the dose level will be expanded to enroll a total of 9 subjects. If no further DLTs are observed in this group of subjects then this dose will be the RP2D.
- If 2 DLTs are observed in the initial 3 subjects, then enrollment to this dose level will be stopped. A DLT review will occur to determine if the dose should be lowered.
- If 3 DLTs are observed, then the dose level will be stopped and the next lower dose will be assessed.

If a subject experiences a DLT during the DLT observation window, the subject will discontinue treatment.

The decision to proceed with a RP2D or to dose reduce will be made in a Dose Level Review Meeting by the Sponsor in conjunction with the investigators after careful consideration of all available safety and laboratory information.

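### The DLT definition calls its list exceptions, but the list names the severe events that should count; read as written, Grade 4 neutropenia is not a DLT and brief Grade 3 neutropenia is

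*Protocol*

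**What the plan says.** Protocol Section 5.2.2 opens: "A DLT is defined as any drug-related hematologic or non-hematologic toxicity Grade 3 or higher, with the following exceptions". Four bullets follow.

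- The first covers Grade 4 nausea, vomiting or diarrhea, and Grade 3 diarrhea "persisting for greater than 3 days despite best supportive care".
- The second reads: "Grade 4 neutropenia or Grade 3 neutropenia persisting for greater than 14 days or Grade 3 neutropenia of any duration with fever".
- The third reads: "For subjects with Grade 2 rash at entry, DLT will be progression to Grade 3 AND a doubling of % BSA involvement".
- The fourth has the same form for subjects who enter with Grade 3 rash.

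The synopsis (Study Treatment) repeats the lead-in and the bullets with slightly different durations: diarrhea "persisting for 3 days despite best supportive care", and "Grade 4 neutropenia or Grade 3 neutropenia persisting for 14 days or Grade 3 neutropenia of any duration with fever". Sections 8.2 and 10.2.1 both point to Section 5.2.2 for the definition.

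Section 5.2.1 attaches a consequence for the subject: "If a subject experiences a DLT during the DLT observation window, the subject will discontinue treatment". It also bases the RP2D and the maximum tolerated dose (MTD) on the DLT count. The final decision is taken at a Dose Level Review Meeting "after careful consideration of all available safety and laboratory information". Section 5.3.1.4 has Phase 1b dosing follow the DLT rules for the first 28 days and brings in Table 1 only afterwards.

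**The concern.** An exception to a definition is something the definition leaves out. On that plain reading, the first two bullets remove the worst gastrointestinal and neutrophil events from the DLT count and leave their milder forms in. Grade 3 nausea would be dose limiting and Grade 4 nausea would not. The rash bullets say what a DLT is, so a single list does two opposite jobs.

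Two things depend on the wording. One is the treatment of the individual subject: a brief Grade 3 neutropenia would end treatment, while a febrile one would have no DLT consequence. The other is the count behind the dose decision, with only 6 to 9 subjects at a level.

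These events are foreseeable. Section 1.8.2.1 lists neutropenia first among frequent Grade 3 or 4 events on ibrutinib monotherapy, and Section 1.8.3.4 calls diarrhea the most frequent non-hematologic event. A subject may enter with an absolute neutrophil count (ANC) of exactly 1.0 x 10^9/L (Section 4.1, criterion 11), and Section 5.3.1.4 puts Grade 3 below 1,000/µL. That is the same value, so any fall from it is Grade 3.

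**Working it through.** **1. The plan's own rule (Section 5.2.1).** A dose becomes the RP2D if DLT incidence is below 33%, and the MTD is exceeded at 3 or more of 9. The counts agree with this:

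- 1/6 = 16.7%: RP2D
- 2/6 = 33.3%: expand to 9
- 2/9 = 22.2%: RP2D
- 3/9 = 33.3%: MTD exceeded

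The rule is consistent. The problem lies in what is counted.

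**2. The two readings of Section 5.2.2 (drug-related events).** As written, a listed event is excluded. As evidently meant, only the listed forms of these toxicities count.

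| Event | As written | As evidently meant |
|---|---|---|
| Grade 4 nausea | not a DLT | DLT |
| Grade 4 vomiting | not a DLT | DLT |
| Grade 4 diarrhea | not a DLT | DLT |
| Grade 3 diarrhea, over 3 days | not a DLT | DLT |
| Grade 4 neutropenia | not a DLT | DLT |
| Grade 3 neutropenia, over 14 days | not a DLT | DLT |
| Grade 3 neutropenia with fever | not a DLT | DLT |
| Grade 3 nausea | DLT | not a DLT |
| Grade 3 vomiting | DLT | not a DLT |
| Grade 3 diarrhea, up to 3 days | DLT | not a DLT |
| Afebrile Grade 3 neutropenia, up to 14 days | DLT | not a DLT |

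Seven are removed and four added: 7 + 4 = 11 event types classified in opposite ways. The rash bullets define themselves as DLTs, so they count on either reading.

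This count takes the persistence clause in the first bullet to qualify Grade 3 diarrhea only. If it also qualifies the Grade 4 events, the seven listed types stay seven in a narrower form. Grade 4 nausea, vomiting and diarrhea of up to 3 days then join the other group: 4 + 3 = 7, so 14 types in all.

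**3. Which reading was meant.** The rash bullets point to the second. So does Section 5.3.1.4, which in Phase 2 modifies the dose for febrile Grade 3 ANC, Grade 4 ANC lasting over 7 days, and persistent Grade 3 or 4 gastrointestinal events. A plan that acts on these in Phase 2 would hardly exempt them in Phase 1b. No text I could read says so. The Section 3.3.1 schema was not in my copy.

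**4. Other dose rules in the 28-day window.**

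- Table 1 starts for Phase 1b subjects only after the window.
- Section 1.8.3.4 sends severe or prolonged gastrointestinal symptoms to Section 5.3.1.4, which in the window leads back to the DLT rules.
- The provisions on hepatic impairment (5.3.1.5), atrial fibrillation (end of 5.3.1.4), CYP3A inhibitors (6.2.1), anticoagulation (6.2.4) and surgery (6.4) address other situations.
- For the listed gastrointestinal and neutropenia events, only the general withdrawal grounds of Section 9.2 remain.

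**5. Where one reclassified subject matters.**

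- 1 to 2 of the first 3: enrollment stops for a DLT review.
- 1 to 2 of 6 (16.7% to 33.3%): 3 more subjects.
- 2 to 3 of 6: the level stops.
- 2 to 3 of 9 (22.2% to 33.3%): from RP2D to MTD exceeded.
- 0 to 1 of 6: no change.

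I put no probability on a changed dose decision. The documents give no rates for these events, and the literal reading both removes and adds DLTs, so even the direction is unknown.

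**6. Synopsis against Section 5.2.2.** The durations differ only for an event of exactly 3 or exactly 14 days.

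**The case against.** The strongest reply is that nobody would apply the literal reading. It makes a milder event dose limiting and a worse one not, and the rash bullets show the purpose. On the evident reading all seven severe types are DLTs, treatment stops, and the gap in the window closes. I accept that the meaning can be recovered. The rule is still applied at multiple centers, and the written text gives the wrong answer. SAP Section 6 says it does not cover the DLT review, so there is no second definition to fall back on.

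The second reply is that the dose decision is not mechanical. The Dose Level Review Meeting sees every Grade 4 event whatever its label, the Sponsor reviews adverse events throughout, and an investigator can stop treatment under Section 9.2. This stands, and it limits the damage. It does not settle which subjects must stop or what count goes to the meeting.

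The third is that Grade 4 neutropenia overstates the gap, because Phase 2 lists a dose action only when it lasts more than 7 days and growth factors are permitted (Section 6.1.1). This is fair for short episodes. Febrile Grade 3 neutropenia and Grade 4 neutropenia beyond 7 days are the clearer examples: each triggers a dose change in Phase 2 and, as written, has no specific rule in the Phase 1b window.

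Finally, the boundary arithmetic would hold for any misclassified event. That is true; it shows what one error can do, not how often one would occur.

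**Conclusion.** The concern holds. Section 5.2.2 and the synopsis state a decision rule that, followed as written, reverses the status of 11 event types, with seven severe ones excluded and four milder ones counted. That count rests on the text as it stands and on the persistence clause applying to Grade 3 diarrhea only. The rule governs both discontinuation and the count behind the RP2D, and for these gastrointestinal and neutropenia events nothing else specific applies in the first 28 days. The intent is recoverable, the review meeting has discretion, and the net effect on the DLT rate is unknown. It should be fixed, but it is not shown to have changed the dose chosen. The synopsis durations are a minor point.

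**What to change.** In Section 5.2.2 and the synopsis, replace the lead-in with: *any drug-related toxicity of Grade 3 or higher, except that the following toxicities count as DLTs only when they meet these thresholds*. This fits all four bullets. Split the first bullet so that it is clear whether the persistence clause applies to Grade 4 events. Align the synopsis with Section 5.2.2 by using more than 3 days and more than 14 days.

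Once corrected, Grade 3 nausea or vomiting in the window will be neither a DLT nor under Table 1. The sponsor should say whether Table 1 applies to such non-DLT events.

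If Phase 1b events have already been adjudicated, re-check the Grade 3 or higher events in the window against the corrected text, and record in the Dose Level Review records which reading was used.

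The drafting cost is one sentence in two places, a bullet split and two durations. The re-check covers 6 to 27 subjects. Under Section 12.14 the change needs a protocol amendment with ethics and site approval, so it is best combined with the next amendment, unless Phase 1b is still enrolling, in which case it should not wait.

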5.3. Study Medication

5.3.1. Ibrutinib

5.3.1.1. Formulation/Packaging/Storage

Ibrutinib capsules are provided as a hard gelatin capsule containing 140 mg of ibrutinib. All formulation excipients are compendial and are commonly used in oral formulations. Refer to the ibrutinib [Investigator's Brochure](#) for a list of excipients.

The ibrutinib capsules will be packaged in opaque high-density polyethylene plastic bottles with labels bearing the appropriate label text as required by governing regulatory agencies. All ibrutinib capsules drug will be dispensed in child-resistant packaging.

Refer to the Pharmacy Manual for additional guidance on study drug storage, dispensing and handling.

Study drug labels will contain information to meet the applicable regulatory requirements.

5.3.1.2. Dose and Administration

Ibrutinib is administered orally once daily. The capsules are to be taken around the same time each day with 8 ounces (approximately 240 mL) of water. The capsules should be swallowed intact and patients should not attempt to open capsules or dissolve them in water. The use of strong CYP3A inhibitors/inducers, and grapefruit and Seville oranges should be avoided for the duration of the study ([Appendix J](#)).

If a dose is not taken at the scheduled time, it can be taken as soon as possible on the same day with a return to the normal schedule the following day. The subjects should not take extra capsules to make up the missed dose.

The first dose will be delivered in the clinic on Day 1, after which subsequent dosing is typically on an outpatient basis. Ibrutinib will be dispensed to subjects in bottles except Week 1 Day 2 and Week 2. Unused ibrutinib must be returned to the site and drug accountability records ([Section 12.8](#)) updated at each visit. Returned capsules must not be redispensed to anyone.

5.3.1.3. Overdose

Any dose of study drug administered in excess of that specified in this protocol is considered to be an overdose. Signs and symptoms of an overdose that meet any Serious Adverse Event criterion must be reported as a Serious Adverse Event in the appropriate time frame and documented as clinical sequelae to an overdose.

There is no specific experience in the management of ibrutinib overdose in patients. No MTD was reached in the Phase 1 study in which subjects received up to 12.5 mg/kg/day (1400 mg/day). Healthy subjects were exposed up to single dose of 1680 mg. One healthy subject experienced reversible Grade 4 hepatic enzyme increases (AST and ALT) after a dose of 1680 mg. Subjects who ingested more than the recommended dosage should be closely monitored and given appropriate supportive treatment.

Refer to [Section 11.4](#) for further information regarding AE reporting.

5.3.1.4. Dose Modification for Adverse Reactions

During Phase 1b, ibrutinib will be stopped according to DLT rules in [Section 5.2.1](#) during the 28 day DLT window. Thereafter, subjects enrolled in Phase 1b will have ibrutinib modified or discontinued according to the guidelines in [Table 1](#).

For Phase 2, the dose of ibrutinib should be modified according to the dose modification guidelines in [Table 1](#) if any of the following toxicities occur:

- Grade 3 ANC (<1,000/ μ L) with an associated temperature $\geq 38.5^{\circ}\text{C}$
- Grade 4 ANC (<500/ μ L) for more than 7 days. Refer to [Section 6.1.1](#) for instruction regarding the use of growth factor support
- Grade 3 thrombocytopenia (<50,000/ μ L) in the presence of Grade ≥ 2 bleeding events
- Grade 4 thrombocytopenia (<25,000/ μ L)

- Grade 3 or 4 nausea, vomiting, or diarrhea if persistent, despite optimal anti-emetic and/or anti-diarrheal therapy
- Any other Grade 4 or unmanageable Grade 3 toxicity attributed to ibrutinib

Table 1: Ibrutinib Dose Modifications

Hematologic Adverse Events	
Occurrence	Action to be Taken
First	Withhold ibrutinib until recovery to an ANC ≥ 750 or platelets $> 25,000$ with no evidence of Grade ≥ 2 bleeding; may restart at original dose level
Second	Withhold ibrutinib until recovery to an ANC ≥ 750 or platelets $> 25,000$ with no evidence of Grade ≥ 2 bleeding; may restart at 1 dose level lower
Third	Withhold ibrutinib until recovery to an ANC ≥ 750 or platelets $> 25,000$ with no evidence of Grade ≥ 2 bleeding; may restart at 1 dose level lower
Fourth	Discontinue ibrutinib ^a
Non-Hematologic Adverse Events	
First	Withhold ibrutinib until recovery to Grade ≤ 1 or baseline; may restart at original dose level
Second	Withhold ibrutinib until recovery to Grade ≤ 1 or baseline; may restart at 1 dose level lower
Third	Withhold ibrutinib until recovery to Grade ≤ 1 or baseline; may restart at 1 dose level lower
Fourth	Discontinue ibrutinib ^a

^a. If ibrutinib is discontinued for toxicity, subject will end the Treatment Phase of the study.

For Grade 3 or 4 atrial fibrillation or persistent atrial fibrillation of any grade, consider the risks and benefits of ibrutinib treatment. If clinically indicated, the use of anticoagulants or antiplatelet agents may be considered for the thromboprophylaxis of atrial fibrillation ([Section 6.2.4](#)).

Dose changes must be recorded in the Dose Administration eCRF. At the Investigator's discretion, the dose of ibrutinib may be re-escalated after 8 weeks of a dose reduction in the absence of a recurrence of the toxicity that led to the reduction.

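### Table 1 sets no fever condition for ending a febrile-neutropenia hold, so at ANC 750–999/µL with persisting fever the hold trigger and the restart condition are both met

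*Protocol*

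**What the plan says.** Protocol Section 5.3.1.4 lists the toxicities that send a Phase 2 subject to Table 1. One is a Grade 3 neutrophil count (ANC below 1,000/µL) "with an associated temperature" of 38.5 °C or more. Another is Grade 3 thrombocytopenia (platelets below 50,000/µL) "in the presence of Grade" 2 or higher bleeding. A catch-all entry reads "Any other Grade 4 or unmanageable Grade 3 toxicity attributed to ibrutinib".

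The first, second and third hematologic rows of Table 1 share one hold condition: "Withhold ibrutinib until recovery to an ANC" of at least 750, or to platelets above 25,000, "with no evidence of Grade" 2 or higher bleeding. After the first occurrence the subject "may restart at original dose level"; after the second and third, "may restart at 1 dose level lower". The fourth row is discontinuation. Neither the rows nor the footnote mention temperature.

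For the earlier phase, once the 28-day DLT window is over, "Thereafter, subjects enrolled in Phase 1b will have ibrutinib modified or discontinued" under Table 1. Inside the window different rules apply: Section 5.2.2 lists Grade 3 neutropenia with fever among the DLT criteria, and Section 5.2.1 has a subject with a DLT stop treatment.

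**The concern.** A hold rule should not release the subject while the event that caused the hold is still present. Here the trigger has two parts, a low count and a fever, and the release tests only the count, at a value below the trigger value. Part of the range that starts a hold therefore also satisfies the condition for ending it. A subject who first triggers at ANC 750–999/µL is already at or above the restart count when the hold begins, so the count sets no minimum hold.

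The stake is subject safety. Inclusion criterion 3 requires systemic glucocorticoids at entry, and Section 1.8.3.5 reports fatal and non-fatal infections with ibrutinib. Neither sample size, power nor type I error is involved.

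**Working it through.** No figure in the plan needs reproducing; the check compares the written conditions. All inputs come from Section 5.3.1.4 and its Table 1.

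| Trigger | Condition to hold | Count to restart | Clinical condition to restart |
|---|---|---|---|
| Grade 3 ANC with fever | ANC <1,000 and T ≥38.5 °C | ANC ≥750 | none on temperature |
| Grade 4 ANC | ANC <500 for more than 7 days | ANC ≥750 | not needed |
| Grade 3 platelets with bleeding | <50,000 and Grade ≥2 bleeding | >25,000 | no Grade ≥2 bleeding |
| Grade 4 platelets | <25,000 | >25,000 | not needed |

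**Step 1, febrile neutropenia.** Take a subject with T ≥38.5 °C and no Grade ≥2 bleeding. Hold: ANC <1,000. Restart: ANC ≥750. Both are met when 750 ≤ ANC ≤ 999, which is 999 − 750 + 1 = 250 integer values. A check of every integer ANC from 0 to 2,000/µL gave the same range and count.

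**Step 2, the other count-based triggers.** ANC <500 and ANC ≥750 exclude each other. So do platelets <25,000 and >25,000. For Grade 3 platelets the restart count (25,000) lies below the trigger count (50,000), as it does for ANC, but the trigger requires Grade ≥2 bleeding and the restart requires its absence, so the two cannot both hold. Only the febrile-neutropenia trigger overlaps its own release.

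**Step 3, other text that might supply a fever condition.** The paragraph after Table 1 covers re-escalation after a dose reduction. Section 6.1.1 covers growth factors. Section 9.2 gives general reasons to stop treatment. The non-hematologic rows (recovery to Grade 1 or lower, or baseline) apply only if the fever or infection is itself judged to fall under the catch-all trigger and attributed to ibrutinib. None of these puts a temperature condition on the neutropenia restart.

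**Step 4, the amended rule.** Restart if (ANC ≥750 and T <38.5 °C) or ANC ≥1,000. In the first branch the fever half of the trigger is false; in the second the count half is false. The overlap with the trigger is 0 at every ANC.

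**Step 5, who is covered.** The trigger list is introduced for Phase 2, about 34 of the roughly 40 subjects planned at the RP2D (Synopsis). Phase 1b subjects past day 28 are sent to Table 1 without a restated trigger list, so the overlap for them is an inference.

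**The case against.** The strongest reply is that Section 5.3.1.4, read whole, still supports holding. While the count is below 1,000 and the fever persists, the trigger remains met; a subject dosed then would at once qualify for another hold. Recovery to 750 is an odd description of someone first held at 800. The restart is optional, Table 1 is called a guideline, Section 9.2 lets the investigator stop in the subject's interest, and the sponsor reviews adverse events continuously. All of this limits the consequence, but it does not remove the overlap. A subject whose count falls below 750 and then climbs through it while still febrile has recovered in any ordinary sense, and the table then permits a restart.

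Stronger readings that a reader might infer are not supported:

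- **That the protocol directs re-dosing during fever.** It says withhold, then may restart.
- **That one febrile episode could take a subject through restarts at 420, 280 and 140 mg.** This would need repeated re-dosing through a continuing fever and each restart counted as a new occurrence. The text does not define occurrence that way, and a new event is the more natural meaning.
- **That the overlap runs from ANC 0 to 999.** It would if the word joining the ANC and platelet limits were taken literally, so that platelets above 25,000 without bleeding released any neutropenic hold. The sensible reading is one limit per cytopenia. The wording deserves tidying, but the point does not rest on it.
- **That a frequency can be stated.** Section 1.8.2.1 lists febrile neutropenia among serious events above 1% in 1,071 monotherapy subjects with B-cell malignancies. That shows the event is foreseeable; it is not a rate for cGVHD.

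**Conclusion.** The gap is real and narrow. For Phase 2 subjects, at ANC 750–999/µL with temperature at or above 38.5 °C, the hold trigger and the stated restart condition are met together in three of the four hematologic rows. This assumes that the ANC and platelet limits each apply to their own cytopenia and that there is no Grade ≥2 bleeding. For Phase 1b subjects after the DLT window the same follows by inference; within the window the DLT rules govern.

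It is a permission that the rule should not give, not an instruction to re-dose. It carries no claimed effect on the response rate and no estimated frequency. I rate it a minor safety-rule correction for the next amendment.

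**What to change.** In the three withhold rows of Table 1 add: *A hold for ANC <1,000/µL with temperature ≥38.5 °C ends when ANC is ≥750/µL and the temperature is <38.5 °C, or when ANC is ≥1,000/µL.* State also that the ANC and platelet limits each apply to the cytopenia that caused the hold.

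The second branch matters. Without it, a subject whose count has fully recovered but who has fever from another cause would stay off drug although the trigger is no longer met. The restart count of 750 need not be raised for subjects whose fever has gone, because they no longer meet the trigger.

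The clause removes the logical conflict only. It sets no fever-free interval, so a subject at 38.4 °C and ANC 750/µL could restart; whether to require an interval is a clinical decision for the sponsor.

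The cost is a short text change in three rows. Some febrile-neutropenia holds will last longer; the documents give no hold durations, so the extra time off drug cannot be estimated.
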